2.4.2 Animal Studies of Sofosbuvir and Velpatasvir During Pregnancy

There are no adequate studies of SOF/VEL in pregnant women. In animal reproduction studies, no evidence of adverse developmental outcomes was observed with the components sofosbuvir or velpatasvir at exposures greater than those in humans at the recommended human dose. During organogenesis in the mouse, rat, and rabbit, systemic exposures (AUC) to velpatasvir were approximately 31 (mice), 6 (rats), and 0.4 (rabbits) times the exposure in humans at the recommended human dose, while exposures to the predominant circulating metabolite of sofosbuvir (GS-331007) were approximately 4 (rats) and 10 (rabbits) times the exposure in humans at the recommended human dose³⁴.

Velpatasvir: Velpatasvir was administered orally to pregnant mice (up to 1000 mg/kg/day), rats (up to 200 mg/kg/day) and rabbits (up to 300 mg/kg/day) on gestation days 6 to 15, 6 to 17, and 7 to 20, respectively, and also to rats (oral doses up to 200 mg/kg) on gestation day 6 to lactation/post-partum day 20. No significant effects on embryo-fetal (mice, rats, and rabbits) or pre/postnatal (rats) development were observed at the highest doses tested. The systemic exposures (AUC) of velpatasvir during gestation were approximately 31 (mice), 6 (rats), and 0.4 (rabbits) times the exposure in humans at the recommended human dose.

Sofosbuvir: Sofosbuvir was administered orally to pregnant rats (up to 500 mg/kg/day) and rabbits (up to 300 mg/kg/day) on gestation days 6 to 18 and 6 to 19, respectively, and also to rats (oral doses up to 500 mg/kg/day) on gestation day 6 to lactation/post-partum day 20. No significant effects on embryo-fetal (rats and rabbits) or pre/postnatal (rats) development were observed at the highest doses tested. The systemic exposures (AUC) of the predominant circulating metabolite of sofosbuvir (GS-331007) during gestation were approximately 4 (rats) and 10 (rabbits) times the exposure in humans at the RHD.

2.5 Rationale for Study Design

There is currently no experience with SOF/VEL in pregnant women, although based on the animal model data submitted to the FDA there were no effects on fetal development observed in mice, rats and rabbits with doses higher than those given

for treatment of hepatitis C in humans. Also, there is reassuring data from our prior study of treatment with LDV/SOF. Unfortunately, LDV/SOF is not approved for treatment of HCV genotypes 2 and 3 and therefore a pan-genotypic regimen in pregnancy is needed. Before larger scale treatment studies can be undertaken, it will be necessary to assess whether the pharmacokinetics of the drugs are similar in pregnant and nonpregnant women, and whether treatment response is similar to that observed in nonpregnant women, given the higher viral loads observed during pregnancy. This study is designed to address those knowledge gaps. We propose a single-arm, single-center, open label Phase 1 study of a 12-week course of SOF/VEL in 10 HCV-infected pregnant women. Treatment will be initiated during the second trimester, reducing the risk of SOF/VEL exposure during organogenesis and ensuring treatment completion by delivery, minimizing the risk of perinatal transmission. Additionally, this will allow adequate time for treatment course completion by delivery.

The study will be completed in 10 or 11 visits (7 maternal visits, delivery visit and 3 infant visits) which should easily align with prenatal and postpartum visits (Table 1). We plan to screen patients between 14+0 and 22+6 weeks of gestation confirmed by ultrasound by the time of their Enrollment visit who are known to have chronic HCV infection. A HCV RNA level to confirm the patient is actively infected with HCV as well as an HCV genotype (when not already available within 3 months of screening visit) will be obtained. A full laboratory evaluation of liver function including CBC, PT/INR, hepatic panel, creatinine, creatinine kinase and lipase will be obtained, to evaluate for renal failure and decompensated cirrhosis. A Hepatitis B Virus (HBV) panel will be performed to test all patients for evidence of current or prior HBV infection before initiation of HCV treatment. Medical history and demographic information will also be collected at screening. If the following inclusion and exclusion criteria are met, then the patient will be enrolled into the study between 23+0 and 25+6 weeks' gestation and initiated on a 12 week course of SOF/VEL.

3 OBJECTIVES

3.1 Primary Objective

1. To compare the plasma pharmacokinetic (PK) parameters of SOF/VEL administered during pregnancy to those of nonpregnant women.

3.2 Secondary Objectives

1. To compare the intracellular concentrations of SOF (GS-461203) during pregnancy to available data from nonpregnant women.
2. To compare the protein binding (free fraction) of VEL in pregnant women to available data from nonpregnant women.

3. To determine the rate of sustained viral response (SVR12), defined by undetectable hepatitis C virus twelve weeks after completion of SOF/VEL treatment for 12 weeks during pregnancy.
4. To evaluate the safety for the mother and for the neonate of hepatitis C treatment with SOF/VEL during pregnancy.

3.3 Exploratory Objective

1. To describe the perspectives of pregnant women with chronic HCV infection screening for a trial of antenatal sofosbuvir/velpatasvir (SOF/VEL) therapy

4 STUDY DESIGN

4.1 Identification of Study Design

This is a single-site, open label, single-arm Phase 1 trial.

4.2 Summary of Major Endpoints

Primary Endpoint:

- **Systemic PK**
 - Systemic exposure of both VEL and SOF will be assessed at three time points:
 - 1) 3 weeks after treatment initiation (intensive sampling);
 - 2) 6 weeks after treatment initiation (sparse sampling);
 - 3) 9 weeks after treatment initiation (intensive sampling).

Secondary Endpoints:

- **Secondary PK endpoints:**
 - Intracellular concentrations of GS-461203 from dried blood spots and peripheral blood mononuclear cells (PBMCs) will be assessed at:
 - 3 weeks \pm 7 days after first dose;
 - 6 weeks \pm 7 days after first dose;
 - 9 weeks \pm 7 days after first dose.
 - Free-fraction of VEL (protein-binding) will be assessed at:
 - 3 weeks \pm 7 days after first dose;
 - 9 weeks \pm 7 days after first dose.
- **Sustained Viral Response (SVR12)**

- HCV RNA viral load will be assessed at 12 weeks after SOF/VEL treatment completion. An undetectable viral load will be considered a SVR12.
- **Maternal Safety**
 - Safety laboratory assessments of blood counts, creatinine, liver function, creatinine kinase and lipase will be measured at the PK1 and PK2 visit (3 and 6 weeks after initiation of SOF/VEL).
 - Pregnancy and delivery outcomes collected prospectively by participant interview and medical record review.
- **Neonate Safety**
 - Major malformations, defined as structural abnormalities with medical, surgical or cosmetic importance
 - Weight, length, and head circumference at birth, 8 weeks, six months and 12 months
 - HCV RNA will be assessed at birth (as available), 1-3 months and 6 months, and then again at 12 months only if detectable viral loads are documented in either of the two previous viral load assessments
 - Neonatal development assessed at 6 months and 12 months

Exploratory Endpoint:

- In depth interviews conducted before enrollment in screened participants and after completion of treatment in enrolled participants

4.3 Description of Study Population

The study population will include 10 pregnant women between the ages of 18-39 years old (inclusive) at Screening who are chronically infected with Hepatitis C virus, genotype 1, 2, 3, 4, 5 or 6 (or any combination of genotypes), as described in Sections 5.2 and 5.3 and infants born to the enrolled participants

4.4 Time to Complete Accrual

The approximate time to complete study enrollment is expected to be 12 months.

4.5 Expected Duration of Participation

The expected duration for maternal participants is approximately 24 weeks, not including the screening window. Infants will be followed for at least a full year after birth; therefore mother-child pairs will be enrolled for approximately one year and 4

months. Maternal study data will be collected from the participant and/or her medical records through the Post Treatment Visit (V7). Maternal participants who have AEs at the Post Treatment Visit (V7) that are clinically significant or related to study product/participation and have not resolved or stabilized will be followed beyond V7 until a clinically acceptable resolution of the AE(s) is confirmed and documented. Similarly, infant study data will be collected through the 12 month follow-up visit (iV3). Infants who have AEs at the iV3 visit that are clinically significant or related to study product/participation and have not resolved or stabilized will be followed beyond iV3 until a clinically acceptable resolution/stabilization of the AE(s) is confirmed and documented.

5 STUDY POPULATION

5.1 Selection of the Study Population

The inclusion and exclusion criteria in Sections 5.2 and 5.3 will be utilized to ensure the appropriate selection of study participants.

5.1.1 Recruitment

There are over 10,000 deliveries at Magee-Womens Hospital (MWH) per year and it is estimated that approximately 1% of women who deliver are actively infected with HCV. HCV-infected pregnant women will be recruited from MWH and antenatal clinics, opiate substitution therapy clinics and recovery programs in Pittsburgh and surrounding areas.

Recruitment will be primarily targeted from the MWH Pregnancy Recovery Center, which was established in 2014 to provide concurrent treatment for opiate dependence (buprenorphine) with prenatal care, which has an estimated retention rate of 90% for weekly opiate substitution and prenatal visits. There are approximately 120 opiate addicted pregnant women who received prenatal care at the Pregnancy Recovery Center per year. The prevalence of HCV infection in this Center is approximately 60%. Recruitment will also be targeted at the Magee-Womens Hospital ambulatory clinic and associated clinics that deliver at Magee-Womens Hospital. In order to engage HCV-infected women in recovery, but not yet engaged in prenatal care, we may also recruit patients from local opiate substitution therapy clinics and recovery programs that treat pregnant women.

Recruitment may also include women who are not receiving care at Magee-Womens Hospital through referrals from health care providers. These women must be willing to travel to Pittsburgh to complete the study visits but may deliver at an outside hospital as information from delivery may be reviewed after obtaining a signed medical record release.

Recruitment materials will be approved by the University of Pittsburgh Institutional Review Board prior to use.

5.1.2 Retention

The importance of retention will be stressed to the participant at each visit as part of protocol adherence counseling. Once a participant is enrolled, the study staff will make every effort to retain the participants in follow-up to minimize possible bias associated with loss-to-follow-up. Any participant that discontinues the study before the PK3 visit is completed or reports missing more than 1 dose per week averaged over the duration of the study will be replaced by recruiting another participant into the study. We anticipate needing to replace no more than one participant.

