DNA	deoxyribonucleic acid
DSMB	Data and Safety Monitoring Board
EAE	Expedited adverse event
FDA	Food and Drug Administration
GCLP	Good Clinical Laboratory Practices
GCP	Good Clinical Practices
HBsAg	Hepatitis B surface antigen
HBV	Hepatitis B Virus
HCV	Hepatitis C Virus
HIV	Human immunodeficiency virus
IDI	In-depth Interview
INR	International normalized ratio
IoR	Investigator of Record
IRB	Institutional Review Board
ISR	Interim Study Review
VEL	Velpatasvir
SOF/VEL	Sofosbuvir/Velpatasvir
mL	Milliliter
MWH	Magee-Womens Hospital
MWRI	Magee-Womens Research Institute
NIAID	National Institute of Allergy and Infectious Disease
NIH	National Institutes of Health
OHRP	Office of Human Research Protections
PBMC	Peripheral Blood Mononuclear Cell
PK	Pharmacokinetic
PoR	Pharmacist of Record
PTID	Participant identification number
RNA	Ribonucleic acid
SAE	Serious adverse event
SOF	Sofosbuvir
SOP	Standard operating procedure(s)
SSP	Study-specific Procedures
UPMC	University of Pittsburgh Medical Center

Phase 1 Pharmacokinetic Trial of Sofosbuvir/Velpatasvir in Pregnant Women with Chronic Hepatitis C Virus Infection

PROTOCOL TEAM ROSTER

University of Pittsburgh Study Team

[name], MSc
UPMC Magee-Womens Hospital
[name]
[name]
[contact]
[contact]
Email: [contact]

[name]

Magee-Womens Research Institute
[name]
[name]
[contact]
[contact]
Email: [contact]

[name], MSc

UPMC Magee-Womens Hospital
[name]
[name]
[contact]
[contact]
Email: [contact]

[name], FAAP, FABM

UPMC Children's Hospital of Pittsburgh
[name]
[name]
Office: [contact]
[contact]
Email: [contact]

University of Colorado

[name], PhD
Skaggs School of Pharmacy and Pharmaceutical Sciences
[name]
[name]
[contact]
[contact]
Email: [contact]

Gilead Sciences Study Team

[name], MPH
Senior Medical Scientist, Liver Disease
Gilead Medical Affairs
[contact]
Email: [contact]

Phase 1 Pharmacokinetic Trial of Velpatasvir/Sofosbuvir in Pregnant Women with Chronic Hepatitis C Virus Infection

PROTOCOL SUMMARY

Short Title:	Treatment of Chronic Hepatitis C during Pregnancy with Sofosbuvir/Velpatasvir
Clinical Phase:	Phase 1
IND Sponsor:	[name], MS
Protocol Chair:	[name], MS
Sample Size:	10 women and their infants (participants who do not complete treatment or report less than 85% adherence will be replaced)

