7.4.4 Post Treatment (V7) Visit

The following procedures will occur at the Post Treatment visit (V7), which should be scheduled 12 weeks ± 4 days from the last dose of study medication. The V7 visit can occur simultaneously with the 8 week Follow-up Visit for the infant (iV1). This is the last scheduled clinic visit for the maternal participant.

Table 8: Post Treatment (V7)

Visit 7 (V7) Post Treatment Visit	
Component	Procedures
Administrative and Regulatory	
 • Review/update locator information • Visit questionnaire • Provide reimbursement • Record/update AEs
Behavioral	
 • Protocol adherence counseling
Clinical	
 • Review/update medical history • Review/update concomitant medications • Perform modified physical examination • Provide available test results from delivery, as applicable
Laboratory	
 • Collect blood 
 • CBC with platelets and differential • Hepatic function panel (AST, ALT, albumin, total and direct bilirubin, alkaline phosphatase) • PT/INR • Creatinine • Lipase • Creatinine kinase • HCV RNA viral load • HCV resistance testing *

*If HCV RNA is detectable, the participant would be asked to return to have HCV resistance testing done, and HCV resistance testing should be done if the participant is still on study medication at time of delivery and study medication was discontinued at the delivery visit because the participant was planning to breastfeed.

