10.2.1 Primary Endpoints: Maternal

The primary endpoints of the study are primary plasma PK parameters (specifically AUC_{tau} , C_{max} , and C_{min}) of VEL, SOF, and GS-331007 assessed at 3 weeks (+/- 7 days of medication initiation).

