10.3 Sample Size

To evaluate the primary objective, we estimate a desired sample size of 10 participants. In order to maintain our sample size, any participant who discontinues treatment during the 12-week treatment period will be replaced. Based on SOF/VEL prescribing information, we will have 87% power to detect a 50% decrease in VEL AUC and >99% power to detect a 2-fold increase. For power calculations we chose this degree of change in VEL AUC because the therapeutic range of SOF/VEL is quite wide and decreases in VEL AUC of up to 50% and increases of up to 2-fold are still associated with efficacy and have acceptable safety/tolerability, respectively.

The FDA does not recommend co-administration of VEL with EFV because it decreases the VEL AUC by >50% [34]. Additionally, this sample size provides an estimated power of 0.82 to detect a 25% change in the AUC of the SOF, given the reported interpatient variability of 35.6% among female patients. Power determinations were performed in SAS v. 9.4 (SAS, Cary, NC).

Any participant that discontinues the study before the PK3 visit is completed or if a participant reports missing more than 1 dose per week averaged over the duration of the study then they will be replaced by recruiting another participant into the study.

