10.4 Participant Accrual and Retention

Pregnant and chronically HCV-infected women who meet the criteria outlined in Section 5 and are interested in participating, will be enrolled into this study. Once a participant is enrolled, the study staff will make every reasonable effort to retain her for the entire study period. Any participant lost to follow-up prior to Visit 7 will be replaced.

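### Replacement is stated with three conflicting time limits and, together with the SVR12 exclusions in 10.5.2, makes SVR12 conditional on completing treatment

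*Combined protocol and SAP*

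**What the plan says.** Replacement is described in four places of the combined protocol and SAP:

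- Protocol Summary, sample size row: "participants who do not complete treatment or report less than 85% adherence will be replaced".
- 5.1.2, repeated in the last paragraph of 10.3: "Any participant that discontinues the study before the PK3 visit is completed", or one who "reports missing more than 1 dose per week averaged over the duration of the study will be replaced".
- 10.3, first paragraph: "any participant who discontinues treatment during the 12-week treatment period will be replaced".
- 10.4: "Any participant lost to follow-up prior to Visit 7 will be replaced". Section 7.4.4 schedules that visit "12 weeks ± 4 days from the last dose of study medication", which is about week 24 for a woman who completes the course.

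The target is fixed in 10.3: "we estimate a desired sample size of 10 participants". Section 5.1.2 expects at most one replacement. Section 10.2.1 has the primary PK parameters "assessed at 3 weeks (+/- 7 days of medication initiation"), while the summary and 4.2 list weeks 3, 6 and 9.

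Section 10.5.2 leaves non-completers and low adherers out of the SVR12 analysis. Section 9.3 requires a permanent stop for a more than 10-fold HCV RNA rise at PK2. Section 7.5 asks women who stop medication to complete all remaining visits. Section 10.5.3 compares safety rates with historical rates and names no analysis set.

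**The concern.** Replacement is meant to preserve ten women for the PK comparison. A trigger that falls after the last primary PK visit does not do that. It acts on later events, namely stopping treatment or being lost, and these bear on SVR12. Combined with 10.5.2, it means the SVR12 result describes women selected for having completed treatment and stayed. A woman whose virus rises on treatment could be stopped under 9.3, replaced under 10.3 and removed from SVR12 under 10.5.2, so that a failure leaves its own denominator. The number enrolled and the set analysed would also depend on which section staff follow. SVR12 is a named secondary objective (3.2), so its denominator should be fixed in advance.

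**Working it through.** **1. The plan's own figure.** Section 10.3 gives power 0.82 for a 25% change in SOF AUC with 10 women and a CV of 35.6%. On the log scale, SD = √ln(1 + 0.356²) = 0.345 and the effect is ln 0.75 = −0.288. At one-sided 5% (assumed from the 90% CI; the plan does not state it), a one-sample normal calculation gives Φ(0.288 × √10 / 0.345 − 1.645) = Φ(0.99) = 0.84. A two-sample t calculation with an assumed 200 controls gives 0.82. The figure is reproducible, and it needs ten women with PK data. Nothing below depends on it.

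**2. The time limits side by side.**

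| Woman | 5.1.2 and end of 10.3 (about week 9) | Summary and start of 10.3 (week 12) | 10.4 (about week 24) |
|---|---|---|---|
| Completes PK3, then stops treatment before week 12 but stays in follow-up | not triggered | replaced | not triggered |
| Completes 12 weeks, then is lost before Visit 7 | not triggered | not triggered | replaced |

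The first row treats doses after a permanent stop as not missed; the plan is silent. If they count as missed, the adherence limit also applies when more than 12 of the 84 doses remain, and the conflict is then confined to stops with 12 or fewer left.

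**3. The adherence limit.** Over 12 × 7 = 84 doses, 12 missed is 1.0 per week and 72/84 = 85.7%: kept under both wordings. Thirteen missed is 1.08 per week and 71/84 = 84.5%: replaced under both. The wordings coincide over the course. They part only if the duration of the study means the roughly 24 weeks of participation in 4.5; the limit is then more than 24 missed doses, or adherence below 60/84 = 71.4%.

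**4. Primary PK status.** Both women in step 2 have reached week 3 (10.2.1) and weeks 3, 6 and 9 (4.2). Under either definition, replacing them adds nothing to the primary endpoint.

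**5. The comparator for SVR12.** Table 2 totals 328 + 238 + 277 + 116 + 35 + 41 = 1035 treated and 323 + 237 + 264 + 116 + 34 + 41 = 1015 with SVR12, so 1015/1035 = 98.07%. The 20 without SVR12 are 13 virologic failures and 7 in the column for other reasons. (The text of 2.4.1 says 12 for the latter; the table balances only with 7.) Leaving out the 7 gives 1015/1028 = 98.74%. The exclusion is worth about 0.7 percentage points there. Among ten women, one exclusion is worth about 9.

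**6. Size here.** Replaced women are counted as no SVR12; intervals are exact 95%.

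| Replaced | All 10 retained respond | 9 of 10 retained respond |
|---|---|---|
| 0 | 10/10 = 100% (69–100%) | 9/10 = 90% |
| 1 | 10/11 = 91% (59–99.8%) | 9/11 = 82% |
| 2 | 10/12 = 83% (52–98%) | 9/12 = 75% |

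Section 10.5.2 expects at least 9 of 10. With the 99% it quotes, that has probability 0.996, but only for a set that excludes non-completers.

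**7. How many replacements.** With loss rate d and recruitment until ten are retained, P(at most one replaced) = (1 − d)¹⁰ × (1 + 10d). At d = 10%, taken from the 90% retention in 5.1.1, this is 0.349 × 2 = 0.70. At an assumed 20% it is 0.107 × 3 = 0.32.

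**The case against.** Replacing women to keep ten with usable PK data is a legitimate choice in a single-arm Phase 1 PK study, and SVR12 is secondary. No section says its trigger is the only one, so the triggers could be read as cumulative. That stands as a possible reading, but it makes the limits in 5.1.2 redundant and still replaces women with complete primary PK data.

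Several stronger readings are tempting and are not supported:

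- A reader might infer that safety results are biased. Section 7.5 keeps women who stop in follow-up, 9.6 does the same after withdrawal, and no text removes a replaced woman's safety data. What stands is that 10.5.3 names no denominator.
- A reader might count four different rules. The summary and the start of 10.3 agree in substance, and the adherence wordings coincide, which leaves three time limits and one adherence limit.
- A reader might take week 3 as the only primary time point and conclude that the PK3 limit serves no purpose. Under 4.2 it does serve the primary endpoint.
- A reader might treat early delivery as a trigger. Section 7.4.3 provides for completing the course after delivery; medication stops only if the woman intends to breastfeed.
- A reader might apply the 50% loss in 2.2. That study was postpartum and is cited as a contrast to pregnancy. In the site's antenatal study all nine treated women were cured.

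Two further limits apply. Table 2 shows no on-treatment virologic failure among 1035, so the route through 9.3 may be rare, although response in pregnancy is what this trial is to establish. Section 10.5.2 does not itself exclude a completer who is later lost; it is silent on a missing Visit 7 result.

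**Conclusion.** The concern holds in this form. The three time limits conflict, and the two later ones replace women who have already reached every primary PK visit. With 10.5.2, SVR12 becomes conditional on completion and adherence and is not like for like with the Phase 3 denominator. With the single replacement the plan anticipates, a reported 100% would be 91% over all treated women; with two, 83%. These figures assume that all ten retained women respond and that replaced women count as no SVR12. They would be milder if a replaced woman were followed and found to have SVR12. The primary PK comparison is not undermined. For safety the gap is an undefined analysis set, not a demonstrated bias.

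**What to change.** - Reconcile the summary, 5.1.2, 10.3 and 10.4 into one replacement rule in 10.3, cited elsewhere, and tie it to PK evaluability for the primary endpoint. Align it with the evaluability text in 7.4.1 and with whichever primary time points are kept from 10.2.1 and 4.2.
- Delete the Visit 7 trigger in 10.4.
- Amend 10.5.2 so that SVR12 is reported for all women who took at least one dose, replaced or not, with a missing result counted as no SVR12. Keep the SVR12 result in completers with adequate adherence as supplementary. Without this amendment the exclusion stays in force whatever the replacement rule says.
- State in 10.5.3 that all treated women form the safety set.
- Report the number replaced, with reasons.

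The cost is protocol wording, with no added visits, samples or treatment changes. The SVR12 figure may look less favourable.
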